5. DATA HANDLING

5.1. Computing Environment

All descriptive statistical analyses will be performed using SAS statistical software (Version 9.4), unless otherwise noted. Medical History and adverse events will be coded using Medical Dictionary of Regulatory Activities (MedDRA) version 25.0 unless otherwise noted. Concomitant medications will be coded using B3 World Health Organization (WHO) Drug Global (March 2022) unless otherwise noted.

5.2. Data Conventions

The following conventions will be used:

- **Period definition:**
 - **Screening Period:** The period prior to Day 1 visit.
 - **Treatment and Observation:** The period from date of vaccine administration to Day 29 visit.
 - **Follow-up:** The period from Day 29 visit to Month 6 visit.
- **Visits:**
 - **Study day 1:** The date of study vaccine administration.
 - **End of Treatment Visit:** The Day 29 visit, or the early discontinuation visit for subjects who withdraw study prior to Day 29.
 - **End of Study Visit:** The last recorded visit date.
 - **Unscheduled visits:** Unscheduled visits results will be listed, but not included in tables or graphs. Rules to map unscheduled visit to analysis visit are defined in Section 5.5.
- **Conversion factors (for derived data calculations):**
 - 1 month = 30.4375 days
 - 1 week = 7 days
- **Baseline characteristics and change from baseline:**
 - Weight values recorded in pounds will be converted to kilograms using the following formula: kilograms = pounds/2.2046.
 - Height values recorded in inches will be converted to centimeters using the following formula: centimeters = inches*2.54.
 - Duration on study (weeks) = (Last visit date – randomization date + 1) / 7.
 - (Absolute) Change from baseline = Value at the time point – Baseline value.

[figure not shown]
- **Adverse events:**
 - **Solicited Adverse Events** will be analyzed using the nominal visit (i.e. the page) on which they were recorded and not according to the date they were entered.
 - **Solicited Adverse Events continuing beyond 7 days:** Solicited AEs continuing beyond 7 days will be reported in the “Adverse Evens (Unsolicited)” page as per Case Report Form (CRF) Completion guidelines and will be identified programmatically as all unsolicited adverse events with answer ‘Yes’ to the question ‘Is this a continuing solicited adverse event?’. The corresponding question in the diary page will not be checked programmatically as it is expected that both sources will be reconciled before DBL so that only the unsolicited page can be used for this analysis.
- **Immunogenicity:**
 - **GMC [or GMT]:** The geometric mean concentration (or titer) = antilog (LSMeans [log₁₀ x]), where x is the assay result and LSMeans is the least square means calculated by the model.
 - **GMR:** The geometric mean ratio = antilog (LSMeans [log₁₀ x]) / antilog(LSMeans [log₁₀ y]), where x and y are the 2 assays results and LSMeans is the least square means calculated by the model.
 - **Fold Ratio:** The ratio between titer/concentration at Day 29 visit and the one at Day 1.
 - **GMFR:** The geometric mean fold ratio = antilog (LSMeans [log₁₀ y]), where y is the assay fold ratio and LSMeans is the least square means calculated by the model.
 - **4-fold increase:** A subject achieved 4-fold increase if fold ratio ≥ 4
 - **BLQ:** Below lower limit of quantification (LLOQ). Per Center for Biologics Evaluation and Research (CBER) criterion, BLQ titer/concentration will be analyzed as:
 - 0.5*LLOQ for calculations of GMT/GMC and GMT/GMC Ratios (GMRs)
 - 1*LLOQ for calculations of fold ratio.
 - **ULOQ:** Upper limit of quantification. Titer/Concentration above ULOQ will be analyzed as:
 - 1*ULOQ for all calculations (GMT/GMC, GMRs, fold-ratio)

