2.2. Sample Size and Power

The sample size is not driven by statistical assumptions for formal hypothesis testing but was based on the safety objective for the study. A total of 200 subjects should provide sufficient information to assess safety and immunogenicity.

The sample size will also be adequate to establish variance of immune response in this target population and plan future studies.

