2.3. Randomization Methodology

A total of 200 subjects are planned to be randomized in a 1:1:1:1 allocation ratio i.e. 50 subjects in each VAX-24 dose arm and 50 in the PCV20 group. There will be no stratification factors.

Treatment will be assigned automatically by the IBM EDC (Electronic Data Capture) system during the study, using a Randomization List generated and uploaded before the enrollment of the first subject.

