6.5.1. GMT/GMC, GMR and GMFR

To estimate the immunogenicity response 1 month first vaccination, OPA titers (log₁₀) and IgG concentrations (mcg/mL) measured at Day 29 visit will be logarithmically transformed for analysis and GMTs/GMCs will be computed with 95% CI for each assay using ANOVA and ANCOVA.

- First model in an ANOVA with log₁₀-transformed concentrations/titers at Day 29 as the dependent variable and treatment group and study site as the fixed effects in the model.
- Second model in an ANCOVA with log₁₀-transformed concentrations/titers at Day 29 as the dependent variable, treatment group and study site as the fixed effects and log₁₀ baseline concentration/titer as the covariate.

The least squares means, and their 95% CIs calculated based on the ANOVA and ANCOVA will be back transformed and reported as the group GMT and GMC values. Comparisons between relevant groups will be based on the estimated adjusted GMTs measured at Day 29 visit for 24 serotypes in VAX-24 (of those 20 in PCV20), and mean square error calculated from the basic ANOVA model using contrast statements. The main comparison of interest will be the three VAX-24 dose levels group versus the PCV20 (20 serotypes) group. However, the three VAX-24 dose groups will also be compared in a pairwise fashion on a serotype-by-serotype basis. No adjustment for multiplicity will be applied and missing data will not be imputed. GMRs will also be calculated from the ANCOVA and ANOVA models.

The analysis of GMFR at Day 29 relative to Day 1 will also be computed using similar models:

- First model in an ANOVA with log₁₀-transformed fold ratio at Day 29 as dependent variable and treatment group and study site as the fixed effects in the model.
- Second model in an ANCOVA with log₁₀-transformed fold ratio at Day 29 as dependent variable, treatment group and study site as the fixed effects and log₁₀ baseline concentration/titer as the covariate.

The least squares means, and their 95% CIs calculated based on the ANOVA and ANCOVA will be back transformed and reported as the group GMFR value.

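### Analysing every value above ULOQ as exactly ULOQ shrinks the GMRs and understates the variance meant for planning later studies; the SAP should count these values and add a censored-model sensitivity analysis where they are common.

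*SAP*

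**What the plan says.** SAP 5.2 (Data Conventions, Immunogenicity) sets results above the assay range to "1*ULOQ for all calculations (GMT/GMC, GMRs, fold-ratio". Results below the range follow a different rule: "0.5*LLOQ for calculations of GMT/GMC and GMT/GMC Ratios (GMRs", but "1*LLOQ for calculations of fold ratio". The lower rule is attributed to a regulator ("Per Center for Biologics Evaluation and Research (CBER) criterion, BLQ titer/concentration will be analyzed as"); the upper rule has no stated source.

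SAP 6.5.1 analyses log10 Day 29 values by ANOVA (treatment, site) and by ANCOVA (plus log10 baseline). The main comparison is each VAX-24 dose against PCV20 on the 20 shared serotypes. In addition, "the three VAX-24 dose groups will also be compared in a pairwise fashion on a serotype-by-serotype basis".

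SAP 2.2, matching Protocol 9.1, says of the sample size: "The sample size is not driven by statistical assumptions for formal hypothesis testing but was based on the safety objective for the study". It then adds: "The sample size will also be adequate to establish variance of immune response in this target population and plan future studies".

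SAP 6.5.2 plans the percentage at or above LLOQ at Day 29 for every serotype and both assays, and reverse cumulative distribution curves at Day 1 and Day 29 by arm and serotype. By-subject listings follow. The visible text contains no count of values above ULOQ, no alternative substitution and no censored-data model.

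**The concern.** A result above ULOQ is right-censored: the true titer is at least ULOQ. Entering it as equal to ULOQ cuts off the upper tail, and cuts off more of it in the arm with the higher response. Three things follow.

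- The higher arm's mean falls by more than the lower arm's, so the GMR moves toward 1 when the SDs are similar. In a dose-finding study, the estimated gain from a higher dose is then too small.
- The residual variance is too small. The plan names this quantity as something the trial will deliver for later studies.
- A subject whose baseline exceeds ULOQ/4 cannot meet the 4-fold criterion, since the largest Day 29 value allowed is ULOQ and ULOQ divided by more than ULOQ/4 is below 4. That subject counts as a non-responder whatever the true rise.

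**Working it through.** **What can be reproduced.** SAP 2.3: "A total of 200 subjects are planned to be randomized in a 1:1:1:1 allocation ratio i.e. 50 subjects in each VAX-24 dose arm"; 200/4 = 50 per arm. The plan gives no SD, GMR, power, ULOQ or censored share, so there is no sample-size figure to reproduce and the size of the effect has to be shown as a range.

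**Assumptions (not in the documents).** Log10 values normal; same SD in both arms, 0.5 to 0.9; true GMR 2.0, so the higher arm is shifted by log10(2) = 0.3010; ULOQ placed so that 1% to 20% of the reference arm exceeds it.

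**Formulas.** For a normal variable with mean μ and SD σ capped at U, with z = (U − μ)/σ:

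- mean m = μΦ(z) − σφ(z) + U(1 − Φ(z))
- second moment = (μ² + σ²)Φ(z) − σ(μ + U)φ(z) + U²(1 − Φ(z))
- variance v = second moment − m²

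**Worked case: σ = 0.6, 10% of the reference arm above ULOQ.** U = 0.6 × 1.2816 = 0.7689.

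- Reference (μ = 0): m = −0.6 × 0.1755 + 0.7689 × 0.10 = −0.0284; v = 0.3013, which is 0.837 of 0.36.
- Other arm (μ = 0.3010): z = 0.7798, so 21.8% lie above ULOQ. m = 0.3010 × 0.7822 − 0.6 × 0.2944 + 0.7689 × 0.2178 = 0.2263; v = 0.2411, which is 0.670 of 0.36.
- Reported GMR = 10^(0.2263 + 0.0284) = 1.80. Pooled variance = (0.837 + 0.670)/2 = 0.753 of true.

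**Range over SD 0.5 to 0.9, true GMR 2.0.**

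| Reference arm above ULOQ | Other arm above ULOQ | Reported GMR | Variance / true | Standardised difference kept |
|---|---|---|---|---|
| 2% | 4.3-7.3% | 1.94-1.96 | 92-95% | over 99% |
| 5% | 9.5-14.9% | 1.88-1.90 | 84-88% | 99% |
| 10% | 17.2-24.8% | 1.78-1.82 | 73-78% | 97-98% |
| 20% | 30.6-40.5% | 1.63-1.68 | 57-63% | 93-95% |

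At 1% the reported GMR is about 1.97 and the pooled SD 98% of true.

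**Detection.** The last column is the capped difference divided by the capped SD, relative to the uncapped value. At SD 0.6 and 50 per arm, two-sided 0.05, power for GMR 2.0 goes from 70.8% to 70.0%, 68.6% and 65.4% at 5%, 10% and 20%.

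**Planning a later study.** With 80% power, n per arm = 2(1.96 + 0.8416)² × variance / (log10 GMR)². At SD 0.6 and GMR 2.0 this is 15.70 × 0.36/0.0906 = 62.4, so 63. Using the capped variance with GMR still at 2.0 gives 54, 47 and 37 at 5%, 10% and 20%. Taking both the variance and the GMR from capped data at 10% gives 15.70 × 0.2711/0.0649 = 65.6, so 66.

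**Does a censored-normal model repair it?** Simulation with 200 subjects, 20 sites (Protocol synopsis: approximately 20), SD 0.6 and all three VAX-24 arms at GMR 2.0. The average estimated GMR moves from 1.98, 1.88 and 1.69 under capping (5%, 10%, 20%) to about 2.1 under the model. Part of the excess over 2.0 is skewness from averaging back-transformed estimates: the standard error is 0.6 × √(2/50) = 0.12 on log10, or 0.276 on the natural log, giving a factor exp(0.276²/2) = 1.04. The maximum-likelihood variance is only about 87% of true, because it divides by n. With 4 treatment and 19 site parameters, p = 23 and (200 − 23)/200 = 88.5%. Multiplying by n/(n − p) returns it to about 99%.

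**The case against.** Several points against the concern stand and limit it.

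- **No document figure shows that censoring will be common.** Without the share above ULOQ the harm may be negligible, as at 1%. Parts of SAP 3.3 are redacted, Section 5.5 is not visible, and laboratory handling of high results may sit in the Central Laboratory Manual. This supports a triggered analysis rather than a change to the main one.
- **A reader might infer that the cap hides a dose response.** It does not, at moderate censoring: the SD shrinks with the difference, and the standardised difference keeps 93-99% of its value across the 5% to 20% cases.
- **A reader might infer that half-LLOQ has the same effect.** It has no fixed direction. At SD 0.3 with 20% of the reference arm below LLOQ, a GMR of 2.0 becomes 2.10 and the pooled SD 108% of true; at SD 0.6 with 50% below, 1.73 and 85%. Half-LLOQ is also not used for the fold ratio. PCV20 values at serotypes 2, 9N, 17F and 20B may lie largely below LLOQ, but those serotypes are outside the main comparison and their planned superiority criterion is the 4-fold rise.
- **A reader might infer that nothing checks the limits.** The planned percentage at or above LLOQ covers the lower limit at Day 29, and the reverse cumulative curves would show pile-up at either limit. What is missing is a count above ULOQ and any measure of its effect on GMR or SD.
- **Toward 1 needs similar SDs.** With PCV20 SD 0.6 and 10% above ULOQ, but VAX-24 SD 0.4, a true GMR of 1.00 is reported as 1.06.
- **The later-study shortfall is conditional.** It arises when a capped SD is paired with an uncapped GMR. Taking both from the same capped data largely cancels the error (66 against 63 per arm).

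**Conclusion.** The concern holds for the ULOQ rule. Under log-normal titers with similar SDs, treating censored values as exact biases GMRs toward 1 and understates the variance. At a true GMR of 2.0 the loss is small with 1-2% of the reference arm above ULOQ and material from about 5%: roughly 1.9, 1.8 and 1.65 at 5%, 10% and 20%, with the variance down to 57-63% of true in the last case. The harm is mainly to the estimates, and the variance matters most because the plan offers it for later design. The 4-fold ceiling for baselines above ULOQ/4 follows from the rule itself; how many subjects it affects is unknown. The documents do not support extending the direction to half-LLOQ, nor a claim that the trial loses its ability to separate doses. This is a worthwhile addition to the SAP and does not invalidate the planned main analysis.

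**What to change.** Keep the SAP 5.2 substitution as the main convention and add to SAP 6.5.1:

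1. A table of n (%) above ULOQ by assay, serotype, arm and visit, and the share of subjects with baseline above ULOQ/4.
2. For any serotype where an arm exceeds a prespecified share above ULOQ (for example 5%), a sensitivity analysis with a censored-normal model using the same treatment, site and baseline terms (SAS PROC LIFEREG), reporting GMT, GMR and residual SD.
3. A statement that the maximum-likelihood variance is multiplied by n/(n − p) before it is used to plan later studies.

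Limits: the model censors the outcome only, so a baseline above ULOQ still enters as ULOQ. The 4-fold ceiling is reported but not removed. The cost is SAP wording, a few more tables and one more standard SAS procedure; no extra samples or subjects.

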5.3. Methods of Pooling Data

Not Applicable.

5.4. Withdrawals, Dropouts, Loss to Follow-up

Subjects who undergo Early Discontinuation after randomization and before Day 1 vaccine administration may be replaced by randomizing an additional subject at the Sponsor's discretion. Subjects who undergo Early Discontinuation after study vaccination will not be replaced.

6. STATISTICAL METHODS

6.1. General Statistical Methods

6.1.1. General Methods

All outputs will be incorporated into Microsoft Word files, sorted, and labeled according to the International Conference on Harmonization (ICH) recommendations, and formatted to the appropriate page size(s).

Tabulations will be produced for appropriate demographic, baseline, safety, and immunogenicity parameters. For categorical variables, summary tabulations of the number and percentage within each category (with the number of subjects with missing data) of the parameter will be presented. For continuous variables, the mean, median, standard deviation, minimum and maximum values will be presented.

Formal statistical hypothesis testing will be performed on immunogenicity parameters with all tests conducted at the 2-sided, 0.05 level of significance. Summary statistics will be presented, as well as 95% confidence intervals (CI) on selected parameters, as described in the sections below.

6.1.2. Definition of Baseline

For all endpoints, baseline is defined as the last non-missing assessment prior to study vaccine administration. Specifically, as per the protocol, baseline evaluations are expected as follows:

- Vital signs: Day 1 prior to study vaccine administration
- Immunogenicity: Day 1 prior to study vaccine administration

6.1.3. Adjustments for Covariates

The randomization in this study will not be stratified.

The following variables will be used for adjustment in immunogenicity analyses:

- For the Analysis of variance (ANOVA), study site will be included as fixed effect in the model.
- For the Analysis of covariance (ANCOVA) and the logistic regression, study site will be included as fixed effect and the log baseline titer will be included as covariate in the model. In case the model does not converge, the log₁₀ baseline titer will be removed from the model and a footnote explicating the change will be added.

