3.4 Study Population

3.4.1 Inclusion Criteria

Subjects must meet all the following criteria to be enrolled:

1. Male or female age 65 or older.
2. Able and willing to complete the informed consent process.
3. Available for clinical follow-up through the last study visit at 6 months after the study vaccination.
4. In good general health as determined by medical history, vital signs, physical examination, and clinical judgment of the investigator. Preexisting medical conditions must be stable as defined by no change in treatment at least 6 weeks prior to study participation.
5. Willing to have blood samples collected, stored indefinitely, and used for research purposes.
6. Able to provide proof of identity to the satisfaction of the study staff completing the enrollment process.

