9.6 Immunogenicity Analysis

9.6.1 GMT/GMR

Immunogenicity analyses will be performed for both OPA (titers) and IgG (mcg/mL). All immunogenicity analyses will be based on the IEP and Exposed Population.

The GMTs and GMCs will be analyzed via linear models. The primary model is an analysis of variance (ANOVA), with logarithmically transformed titers (\log_{10}) as the dependent variable and treatment group and study site as the fixed effects in the model. The results included in the main tables of this report will be based on this basic ANOVA model. As a secondary analysis, to remove the effect of baseline concentration on the GMTs, an analysis of covariance (ANCOVA) will also be performed. The ANCOVA includes treatment group and study site as the fixed effects and \log_{10} baseline titer as the covariate in the model. The rationale for including baseline values as a covariate is that prior data have shown vaccine response is correlated with baseline antibody levels.

The least squares means and their 95% confidence intervals (CIs) calculated based on the ANOVA and ANCOVA will be back transformed and reported as the group GMT and GMC values (adjusted for the mean baseline in the case of the ANCOVA). GMRs will also be calculated from the ANCOVA and ANOVA models.

Comparisons between relevant groups will be based on the estimated adjusted GMTs measured at Day 29 for 24 serotypes in VAX-24 (of those 20 in PCV20), and mean square error calculated from the basic ANOVA model using contrast statements. The analysis of GMFR relative to Day 1 will also be computed using similar models.

The main comparison of interest will be the three VAX-24 dose levels group versus the PCV20 (20 serotypes) group. However, the three VAX-24 dose groups will also be compared in a pairwise fashion on a serotype-by-serotype basis. No adjustment for multiplicity will be applied and missing data will not be imputed.

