6.2.2. Demographic Characteristics

Demographic characteristics at enrollment (i.e., at the time of informed consent) will be presented. Summary will include the following: age, sex, ethnicity, race, height, weight, body mass index.

Medical history will be coded using Medical Dictionary for Regulatory Activities (MedDRA) and summarized alphabetically by System Organ Class (SOC) and Preferred Term (PT).

Table summaries to be produced by treatment group and overall and repeated for the Randomized Population, the Safety Population and the Immunogenicity Evaluable Population.

Demographic characteristics and medical history data will also be provided in data listings on the Randomized Population.

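### The ANCOVA for the antibody responses leaves out age, which is recorded for everyone; adding it is a cheap possible gain in precision, not the removal of a bias.

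*SAP*

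**What the plan says.** SAP 6.1.3 sets out the adjustment with "The following variables will be used for adjustment in immunogenicity analyses". The list has two entries.

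- ANOVA: "For the Analysis of variance (ANOVA), study site will be included as fixed effect in the model".
- ANCOVA and logistic regression: "study site will be included as fixed effect and the log baseline titer will be included as covariate in the model". If a model does not converge, the baseline titer is dropped and a footnote says so.

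SAP 6.5.1 repeats the ANCOVA for GMT/GMC and for GMFR, with "treatment group and study site as the fixed effects and log₁₀ baseline concentration/titer as the covariate"; GMRs are also taken from it. SAP 6.5.2 gives the logistic model the same terms. Protocol 9.6.1 and 9.6.2 specify the same models, so the two documents agree. Protocol 9.6.1 makes the ANOVA the primary model and the source of the main tables, with the ANCOVA secondary. SAP 6.5.2 draws the GMT and GMC bar plots and the forest plots from the ANOVA.

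On age, SAP 6.2.2 says: "Summary will include the following: age, sex, ethnicity, race, height, weight, body mass index". SAP 4.1 makes demographic data part of the definition of the Randomized Population. Protocol 3.4.1 admits "Male or female age 65 or older", with no upper limit. SAP 2.3 states "There will be no stratification factors", and SAP 6.1.5 plans no subgroup analysis. Age is therefore used descriptively only. Neither document gives a reason for leaving it out of the models.

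**The concern.** Protocol 9.6.1 justifies its one continuous covariate by a known correlation between baseline antibody and vaccine response. Age is another baseline value, fully recorded before vaccination, in a population with an open upper end. Neither document considers it against that standard, although site takes about 19 degrees of freedom.

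Two things are at stake, both in the adjusted analysis. If age explains part of the Day 29 titer beyond site and baseline, that variation stays in the residual and the ANCOVA intervals are wider than they need be. And with 50 subjects per arm and no stratification, the arms can differ in mean age by chance; an analysis meant to adjust for baseline differences would leave that one uncorrected.

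**Working it through.** The plan states no power, effect size or SD for immunogenicity. The only figure to reproduce is the allocation: 200 / 4 = 50 per arm, which agrees with SAP 2.3.

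**Inputs from the documents.** 200 subjects in 4 arms (SAP 2.3); approximately 20 sites (Protocol synopsis); ANCOVA terms treatment, site and log10 baseline (SAP 6.5.1).

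**Assumptions not in the documents.** The partial correlation r of age with log10 Day 29 titer, given site and baseline, is taken as 0 to 0.3. The residual SD of log10 titer is taken as 0.5 to 1.0, with 0.6 as an example. All 200 subjects are taken as evaluable, at 20 sites.

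**1. Precision.** Residual degrees of freedom without age are 200 − 4 − 19 − 1 = 176, and with age 175. The approximate variance ratio is (1 − r²) × 176/175.

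| r | Variance ratio | Change in effective sample size (1/ratio − 1) | Ratio of CI half-widths (square root) |
|---|---|---|---|
| 0 | 1.006 | −0.6% | 1.003 |
| 0.1 | 0.996 | +0.4% | 0.998 |
| 0.2 | 0.965 | +3.6% | 0.983 |
| 0.3 | 0.915 | +9.3% | 0.957 |

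Adjustment breaks even where 1 − r² = 175/176, so r = √(1/176) ≈ 0.08.

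**2. Chance imbalance.** In units of the age SD, the difference in mean age between two arms of 50 has a standard error of √(2/50) = 0.20. A difference above 0.4 SD is a two-standard-error event: 4.6% for one VAX-24 versus PCV20 contrast, and about 11% for at least one of the three (by simulation).

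**3. Size of such an imbalance against the interval.** With r = 0.2 and SD 0.6, a 0.4 SD imbalance shifts the log10 GMR by 0.4 × 0.2 × 0.6 = 0.048, a factor of 10^0.048 = 1.12. The 95% half-width is about 1.97 × 0.6 × 0.20 = 0.236 log10, a factor of 1.72. The shift is 0.048 / 0.236, about one fifth of the half-width.

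The SD cancels from that comparison: (0.4 × r × SD) / (1.97 × 0.20 × SD) ≈ r. For r from 0.1 to 0.3, an imbalance of this size therefore moves the estimate by about 10% to 30% of the half-width. Over SD 0.5 to 1.0 the shift factor runs from 1.05 to 1.32, against interval factors of 1.58 to 2.48.

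**The case against.** The case for leaving the plan alone is strong in several respects.

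- **The omission is pre-specified and consistent.** Protocol and SAP agree, and the chosen covariate has a stated reason. No document shows that Day 29 response varies with age among people already 65 or older, and baseline titer may carry part of any age effect. This stands: the gain is conditional. Sex or body mass index could be proposed on similar grounds.
- **Randomisation deals with age in expectation.** A reader might infer that, without stratification, the GMRs are biased by age. They are not. Linear-model GMRs stay unbiased and their intervals already cover chance imbalance, as step 3 shows.
- **A shared shift across serotypes is not established.** Because the same subjects supply every serotype, a reader might infer that one age imbalance moves all 24 ratios for a dose in one direction. That requires an age effect of the same sign for every serotype, which the documents do not support. The main comparison with PCV20 also covers 20 serotypes, not 24.
- **The headline outputs would not move.** Main tables and forest plots come from the ANOVA, and SAP 6.5.1 bases group contrasts on the ANOVA mean square error. Age in the ANCOVA changes only ANCOVA results.
- **The logistic model is already stretched.** It carries about 20 sites, with 200 / 20 = 10 subjects each on average, and SAP 6.1.3 foresees non-convergence. The 0.6% cost is a linear-model figure and does not describe the risk there.
- **An imbalance would be visible.** Age is tabulated by arm, including in the Immunogenicity Evaluable Population, and the protocol synopsis allows supplementary analyses.

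These points limit the concern to the ANCOVA and to precision. They do not remove it: a supplementary analysis chosen after an imbalance is seen is weaker than one fixed beforehand, and the cost of fixing it now is very small.

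**Conclusion.** The point holds as a minor improvement to the secondary, adjusted analysis. The ANCOVA for GMT/GMC, GMR and GMFR leaves out a baseline variable already held for every randomised subject. The consequence is a possible loss of precision and an uncorrected chance imbalance, not bias and not an error in the plan.

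The size runs from a 0.6% variance cost at r = 0 to a gain of about 9% in effective sample size at r = 0.3, with benefit once r exceeds about 0.08. This rests on assumed correlations; if age adds nothing beyond baseline titer and site, there is no gain. No conclusion of the trial is shown to depend on it.

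**What to change.** Before unblinding:

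1. In SAP 6.1.3 and 6.5.1, add age at enrolment, continuous in years, as a covariate in the ANCOVA for GMT/GMC, GMR and GMFR, beside site and log10 baseline. Record the departure from Protocol 9.6.1 in SAP section 7.
2. Leave the ANOVA as it is.
3. Add age to the logistic model in SAP 6.5.2 only if the non-convergence rule in SAP 6.1.3 is extended so that age is removed first, before log10 baseline titer.

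The cost is SAP wording and one model term, with no new data. The ANCOVA gives up one of about 176 residual degrees of freedom, about 0.6% in variance if age is unrelated to response.
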